#### **7.1.3 Body composition**

---

We will use the InBody 770 Body Composition Analyzer to assess patients' body composition. The patients steps onto the apparatus and holds on to the hand grips. The InBody 770 scanner uses six different electromagnetic frequencies to obtain 30 impedance measurements and three frequencies to obtain 15 resistance measures. The results can be integrated to yield body total water content, total fat content, percent fat, the ratio of extracellular water to intracellular water [measuring oedema], and visceral fat.

#### **7.1.4 Quality of life**

---

Quality of life will be examined at baseline and at the end of the study using two validated questionnaires; the SF36 and the EQ 5D 3L EuroQoL questionnaire. The SF-36v2 is a 36-item general health-related quality of life instrument that has 36 questions that contribute to 8 domains or scale scores of physical functioning, role-physical, bodily pain, general health, vitality, social functioning, and role-emotional and mental health. The EQ 5D 3L EuroQoL questionnaire consists of 2 pages, the EQ-5D descriptive system and the EQ visual analogue scale. The quality of life questionnaires (in Norwegian) can be found in appendix B.

#### **7.1.5 Cognitive function**

---

Cognitive function will be assessed with the Cambridge Neuropsychological Test Automated Battery (CANTAB). The CANTAB test battery is performed electronically on a dedicated tablet. CANTAB is language-independent, culturally neutral, and requires no technical knowledge or prior familiarity with computers. It helps to determine an individual's cognitive health across five key domains and includes an integrated depression scale to assess the current mood of the person taking the test.

The cognitive domains assessed are:

- Executive function - Central control, planning, strategy, and flexible thinking
- Processing speed - The ability to perform mental tasks quickly and efficiently
- Attention - The ability to concentrate and actively process information
- Working memory - How we hold information while processing or acting on it
- Episodic memory - Memory of events and experiences: what happened, where and when?

Benefits of using the CANTAB platform includes dedicated courses for the staff administering the test, the highly accurate and validated evaluation of cognitive performance, the good discriminatory

ability, even in high-functioning individuals, and the dedicated technical support. CANTAB is already accepted for use in research at Oslo University Hospital, and was used in the world-wide Ebbinghausen study that assessed cognitive function in patients treated with evolocumab vs placebo.

### 7.1.6 Blood samples

---

We will draw blood samples for biobanking at baseline, prior to study drug infusion, and at 6 months. For biobanking, 18 ml blood should be drawn into tubes containing EDTA as the anticoagulant, 6 ml into tubes with citrate as the anticoagulant and 6 ml into tubes without additives. The tubes with EDTA and citrate should be put on ice immediately and be centrifuged at 3700 rotations/min for 20 minutes. The tubes without additives should be left at room temperature for 1-2 hours prior to centrifugation at 3500 rotations/min for 15 minutes. The tubes containing citrate as the anticoagulant should be put on ice immediately. The resulting plasma and serum, respectively, should be stored in multiple aliquots (at least four aliquots of serum and six aliquots of plasma per patient per visit), and labelled with the unique trial subject number, and the letter A signifying baseline, and the letter B signifying the end-of-treatment visit. The samples should be stored at -80 degrees Celsius until analysis.

Blood samples for safety will be collected at baseline, and 6 months after randomisation (end-of-study). These blood samples will be drawn and analysed at the study sites as per clinical routine. Troponin values will be used for endpoint analyses.

NT-proBNP will be assayed on a MODULAR platform (Roche Diagnostics, Basel, Switzerland). Plasma levels of CRP will be determined by a high-sensitivity particle-enhanced immunoturbidimetric assay (Tina-quant CRP [Latex] HS, Roche Diagnostic, Basel, Switzerland). TnT will be assessed using a high-sensitive immunoassay (Roche hs-TnT).

## 7.2 Safety and tolerability

---

Safety will be monitored by the assessments described below as well as the collection of AEs at every visit. Significant findings that are present prior to the signing of informed consent must be included in the relevant medical history/ current medical condition page of the CRF. For details on AE collection and reporting, refer to Section 8.

For the assessment schedule, refer to Flow chart in Section 6.1.

Physical examinations will be performed at baseline and after 6 months. Vital signs including heart rate and blood pressure will be recorded before, during, and after study drug infusion. Monitoring must be especially vigilant with regard to signs of acute hypersensitivity reactions/abrupt hypotension.

Blood samples for safety analyses will be drawn at baseline and after 3 and 6 months. Local laboratory cut-points for normal values will be used for safety analyses. Haemoglobin; white blood cell count, platelet count; serum potassium; serum sodium; glucose, glycosylated haemoglobin (HbA1c); creatinine; ALT; bilirubin; albumin; INR; CRP; N-terminal pro-B-type natriuretic peptide (NT-proBNP); total cholesterol; ferritin; transferrin, serum iron and total iron binding capacity will be evaluated at each visit. In addition, blood samples for the measurement of iron stores will be drawn 3 months after study drug administration.

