### 8.1.1 Adverse event (AE)

An AE is any untoward medical occurrence in a patient administered a pharmaceutical product and which does not necessarily have a causal relationship with this treatment.

An adverse event (AE) can therefore be any unfavourable and unintended sign (including an abnormal laboratory finding), symptom, or disease temporally associated with the use of a medicinal (investigational) product, whether or not related to the medicinal (investigational) product.

The term AE is used to include both serious and non-serious AEs.

If an abnormal laboratory value/vital sign are associated with clinical signs and symptoms, the sign/symptom should be reported as an AE and the associated laboratory result/vital sign should be considered additional information that must be collected on the relevant CRF.

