## 8.3 Recording of adverse events

---

If the patient has experienced adverse event(s), the investigator will record the following information in the CRF:

The **nature of the event(s)** will be described by the investigator in precise standard medical terminology (i.e. not necessarily the exact words used by the patient).

The **duration of the event** will be described in terms of event onset date and event ended date.

The **intensity** of the adverse event will be categorised as mild / moderate / severe / life-threatening / death according to Common Terminology Criteria for Adverse Events version 4.0:

- Mild: asymptomatic or mild symptoms; clinical or diagnostic observations only; intervention not indicated;
- Moderate; minimal, local or non-invasive intervention indicated; limiting age-appropriate instrumental activities of daily life;
- Severe: Severe or medically significant but not immediately life-threatening; hospitalisation or prolongation of hospitalisation indicated; disabling; limiting self-care activities of daily life;
- Life-threatening consequences: urgent intervention indicated.

The **causal relationship** of the event to the study medication will be assessed as one of the following:

- Unrelated: There is not a temporal relationship to investigational product administration (too early, or late, or investigational product not taken), or there is a reasonable causal relationship between non-investigational product, concurrent disease, or circumstance and the AE.
- Unlikely: There is a temporal relationship to investigational product administration, but there is not a reasonable causal relationship between the investigational product and the AE.
- Possible: There is reasonable causal relationship between the investigational product and the AE. Dechallenge information is lacking or unclear.
- Probable: There is a reasonable causal relationship between the investigational product and the AE. The event responds to dechallenge. Rechallenge is not required.
- Definite: There is a reasonable causal relationship between the investigational product and the AE.

Action taken: **Which investigations/medical procedures/treatments that are initiated as a result of the adverse event.**

The **outcome** of the adverse event – whether the event is resolved or still ongoing.

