9.3 Exploratory Efficacy Analyses

Exploratory analyses of between-group differences in inflammatory parameters and parameters pertaining to iron metabolism, such as Hepcidin, Interleukin 6 and the ferritin index will be performed by ANCOVA or repeated test t-tests, if necessary after log-transformation to meet the requirements of the test.

10 Safety Analyses

Safety analyses will include tabulation of type and frequency of all adverse events. Any value of safety laboratory parameters outside normal ranges will be identified. The final report will include the absolute number of adverse and severe adverse events in each group. The results will be reported for the Safety Population only. The summary statistics will be produced in accordance with section 8.

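### Safety laboratory values are flagged against normal ranges without reference to the patient's own baseline, and the iron indices sit in the same list, so the out-of-range listing dilutes any real laboratory signal

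*Protocol*

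**What the plan says.** Protocol 7.2 lists the safety panel and sets the standard for reading it: "Local laboratory cut-points for normal values will be used for safety analyses". The panel has 19 analytes. Fifteen are general (haemoglobin, white cells, platelets, potassium, sodium, glucose, HbA1c, creatinine, ALT, bilirubin, albumin, INR, CRP, NT-proBNP, total cholesterol). Four are iron indices (ferritin, transferrin, serum iron, total iron binding capacity).

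SAP section 10 gives the analysis rule, in the same words as Protocol 10.5: "Any value of safety laboratory parameters outside normal ranges will be identified". Neither document adds a comparison with baseline, a shift table, a grade or a definition of treatment-emergent abnormality for laboratory values. Protocol 6.2.1 and 7.2 both have the panel drawn at baseline.

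Two other safety outputs are planned:
- Protocol 10.5 summarises safety data by treatment group with means, medians, ranges and standard deviations. SAP section 10 refers to SAP section 8 for similar summaries. Neither mentions within-patient change.
- Adverse events are tabulated separately: "The final report will include the absolute number of adverse and severe adverse events in each group". Protocol 8.1.1 defines an adverse event as "any unfavourable and unintended sign (including an abnormal laboratory finding), symptom, or disease" with a temporal association to the product.

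The sections disagree about 3 months. Protocol 7.2, the table in 6.1 and SAP 5.2 place safety samples there. Protocol 6.2.2 names only haemoglobin and four iron measures, assayed after the end of the study. Protocol 7.1.6 gives safety samples at baseline and 6 months only.

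**The concern.** Safety and tolerability is a stated secondary objective, and the laboratory listing is one of the few places where an unexpected effect of the infusion could show. Three kinds of value that say nothing about new harm enter that listing.

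1. **Values already abnormal before infusion.** Every patient is iron deficient by the entry criterion. Protocol 1.2 describes low-grade inflammation in cardiac allograft recipients. Section 1 names renal failure among their reasons for iron deficiency, and only eGFR below 15 ml/min or renal replacement therapy is excluded. Out-of-range iron indices, CRP or creatinine at baseline are therefore foreseeable, although no local ranges or frequencies are given.
2. **Values abnormal by chance**, which 19 analytes per panel will produce.
3. **Changes in the four iron indices**, which are the drug's intended action. Iron may remove flags by correcting low values or add flags by carrying values above the range. Either way they sit beside possible harms.

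If the flags are tallied by arm without reference to baseline, a real excess of new abnormality is diluted and may be missed.

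**Working it through.** **The plan's own figures.** The documents give no rate for laboratory abnormality, so there is no figure on this point to reproduce. The primary sample size does reproduce: 2 × (1.960 + 0.842)² × (2.5/1.5)² = 43.6, hence 44 per group. It is unaffected. From 100 patients randomised 1:1, I use n = 50 per arm.

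**Step 1: chance flags.** Assume each analyte is out of range with probability p, independently. For k analytes, P(at least one flag) = 1 − (1 − p)^k, and the expected number is kp.
- k = 19, p = 0.05: 1 − 0.95^19 = 62 %; expected 0.95 flags per patient per panel.
- k = 15 (without iron indices), p = 0.05: 1 − 0.95^15 = 54 %.
- k = 19, p from 0.025 to 0.10: 38 % to 87 %.

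The total in 100 patients depends on which section governs 3 months:
- 6 months only: 19 × 0.05 × 100 = 95.
- Five measures at 3 months plus the full panel at 6 months: 24 × 0.05 × 100 = 120.
- Full panel at both visits: 38 × 0.05 × 100 = 190.

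Analytes are correlated, so these are orders of magnitude only.

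**Step 2: dilution by pre-existing abnormality.** For one analyte, let a share b be abnormal at baseline in both arms and stay so. Among baseline-normal patients, let c0 = 5 % (placebo) and c1 = 25 % (iron) become abnormal. All these rates are assumed.

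- Counting every abnormal value: p0 = b + (1 − b)c0 and p1 = b + (1 − b)c1, with 50 per arm.
- Counting shifts from a normal baseline: c0 against c1, with 50(1 − b) per arm.
- Power (two-sided 5 %, pooled variance under the null) = Φ{[|p1 − p0| − 1.96√(2p̄(1 − p̄)/n)] / √([p0(1 − p0) + p1(1 − p1)]/n)}.

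Worked for b = 0.30:
- Every abnormal value: p0 = 0.30 + 0.70 × 0.05 = 0.335; p1 = 0.30 + 0.70 × 0.25 = 0.475; risk ratio 0.475/0.335 = 1.42. Power = Φ[(0.140 − 1.96 × 0.0982)/0.0972] = Φ(−0.54) = 29.5 %.
- Shifts only, n = 35: power = Φ[(0.200 − 1.96 × 0.0854)/0.0819] = Φ(0.40) = 65.5 %.

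| Abnormal at baseline | p0, p1, every abnormal value | Risk ratio | Power | Risk ratio, shifts only | Power |
|---|---|---|---|---|---|
| 0 % | 0.050, 0.250 | 5.0 | 80.9 % | 5.0 | 80.9 % |
| 10 % | 0.145, 0.325 | 2.24 | 56.6 % | 5.0 | 76.6 % |
| 30 % | 0.335, 0.475 | 1.42 | 29.5 % | 5.0 | 65.5 % |
| 50 % | 0.525, 0.625 | 1.19 | 17.0 % | 5.0 | 50.8 % |

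The two rules agree when nobody is abnormal at baseline and diverge as b rises. The plan specifies no test of these counts, so power here measures how visible a signal would be.

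**The case against.** The strongest reply is that the listing is not the only safety comparison. Protocol 10.5 and SAP section 8 give by-arm continuous summaries, and CRP and NT-proBNP have their own between-arm tests in SAP 9.2.1. A large shift would be seen there. Placebo control with 1:1 randomisation also balances baseline and chance abnormality in expectation. Both arguments stand: they limit the point to noise in one output. They do not repair that output, because group summaries contain no within-patient change and balance does not prevent dilution.

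A reader might go further and infer that the adverse event counts per arm are swamped by laboratory flags. The definition does mention laboratory findings, and the mild grade in Protocol 8.3 admits "asymptomatic or mild symptoms; clinical or diagnostic observations only; intervention not indicated". The documents do not support that inference:
- Tabulating adverse events and identifying out-of-range values are separate outputs. No text enters each flagged value as an event.
- An event must be unfavourable and unintended, which keeps correction of iron markers out.
- With symptoms, the symptom is the event: "If an abnormal laboratory value/vital sign are associated with clinical signs and symptoms, the sign/symptom should be reported as an AE".
- Pre-existing findings are partly handled. Protocol 7.2 says "Significant findings that are present prior to the signing of informed consent must be included in the relevant medical history", and Protocol 8.2 starts collection at study treatment.

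It remains true that no rule says when an isolated out-of-range value becomes an event. How to settle that is a debatable safety-reporting choice, and nothing here requires changing the definition in 8.1.1.

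Nor can one infer that the iron indices tilt the listing in iron's favour. Without local ranges or expected values, the net direction of those flags is unknown.

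**Conclusion.** The point holds for the laboratory listing only, and it is minor. As written, the rule ignores a baseline panel that the trial already draws, and it puts the drug's pharmacodynamic targets among the safety flags. Under the assumed rates, a fivefold excess of new abnormality would appear as a risk ratio of about 2.2, 1.4 or 1.2 with 10, 30 or 50 % abnormal at baseline. Power would fall from 77, 66 or 51 % with shifts to 57, 30 or 17 %.

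These figures rest on baseline abnormalities that persist, equal baseline frequency in the arms, complete follow-up of 50 per arm and invented rates of new abnormality. They show direction and rough size and do not predict this trial. The primary endpoint, the sample size and the adverse event tabulation are unaffected.

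**What to change.** In SAP section 10, and in Protocol 7.2 and 10.5 to match:

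1. For each analyte and each direction (above or below range), tabulate by arm the number of patients with a new abnormality (in range at baseline, out of range at follow-up) or a worsened one, as a shift table with the between-arm difference and 95 % confidence interval. Fix the criterion for worsening from an abnormal baseline before the code is opened.
2. Report ferritin, transferrin, serum iron and total iron binding capacity in a separate pharmacodynamic table, outside the safety flags.
3. Reconcile Protocol 6.1, 6.2.2, 7.1.6 and 7.2 and SAP 5.2 on which safety samples are taken at 3 months, so that the visits entering the table are known.

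Shift tables remove pre-existing abnormality. Chance abnormality remains, but the placebo column then shows its size. The cost is wording and some programming: baseline and 6-month values are already collected, and Protocol 10.4 allows changes to the plan until database lock.

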## 8 Safety monitoring and reporting

---

The investigator is responsible for the detection and documentation of events meeting the criteria and definition of an adverse event (AE) or serious adverse event (SAE). Each patient will be

instructed to contact the investigator immediately should they manifest any signs or symptoms they perceive as serious.

The methods for collection of safety data are described below.

## 8.1 Definitions

---

### 8.1.1 Adverse event (AE)

An AE is any untoward medical occurrence in a patient administered a pharmaceutical product and which does not necessarily have a causal relationship with this treatment.

An adverse event (AE) can therefore be any unfavourable and unintended sign (including an abnormal laboratory finding), symptom, or disease temporally associated with the use of a medicinal (investigational) product, whether or not related to the medicinal (investigational) product.

The term AE is used to include both serious and non-serious AEs.

If an abnormal laboratory value/vital sign are associated with clinical signs and symptoms, the sign/symptom should be reported as an AE and the associated laboratory result/vital sign should be considered additional information that must be collected on the relevant CRF.

### 8.1.2 Adverse events of special interest (AESI)

In general, AESIs are AEs that occur in categories of special interest with regard to determining the benefit/risk profile and overall safety of a drug. Two kinds of AEs are of particular concern regarding intravenous iron infusions:

- Hypersensitivity/anaphylactic reactions: Infusion with Monofer® can result in acute hypersensitivity reactions characterised by hypotension and signs of anaphylaxis. These reactions may occur even in patients who have had previous, uneventful iron infusions, and are more common in patients with allergic diatheses or autoimmune diseases.
- Skin discolouration: Paravenous leakage may cause skin irritation and long-lasting discolouration.

### 8.1.3 Serious adverse event (SAE)

Any untoward medical occurrence that at any dose:

- Results in death
- Is immediately life-threatening
- Requires in-patient hospitalisation or prolongation of existing hospitalisation
- Results in persistent or significant disability or incapacity
- Is a congenital abnormality or birth defect
- Is an important medical event that may jeopardise the subject or may require medical intervention to prevent one of the outcomes listed above.

Medical and scientific judgment is to be exercised in deciding on the seriousness of a case. Important medical events may not be immediately life-threatening or result in death or hospitalisation, but may jeopardise the subject or may require intervention to prevent one of the listed outcomes in the definitions above. In such situations, or in doubtful cases, the case should be considered as serious. Hospitalisation for administrative reason (for observation or social reasons) is allowed at the investigator's discretion and will not qualify as serious unless there is an associated adverse event warranting hospitalisation.

### 8.1.4 Suspected unexpected serious adverse reaction (SUSAR)

**Adverse Reaction:** all untoward and unintended responses to an investigational medicinal product related to any dose administered;

**Unexpected Adverse Reaction:** an adverse reaction, the nature or severity of which is not consistent with the applicable product information as provided in the Monofer® SPC.

**Suspected Unexpected Serious Adverse Reaction:** SAE (see section 8.1.3) that is unexpected and possibly related to the investigational medicinal products. Any SAE not mentioned in the investigational medicinal product SPC, paragraph 4.8, is to be considered a suspected unexpected serious adverse reaction (SUSAR).

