### 8.4.1 Adverse events, adverse events of special interest and serious adverse events

---

All adverse events and serious adverse events that should be reported as defined in section 8.1.1 will be recorded in the patient's CRF. SAEs must be reported by the investigator to the sponsor, Oslo University Hospital, within 24 hours after the site has gained knowledge of the SAE. The Serious Adverse Event Report Form must be completed, documented in the CRF, signed and sent to [name]. The initial report shall promptly be followed by detailed, written reports if necessary. The initial and follow-up reports shall identify the trial subjects by unique trial code numbers assigned to the latter. The sponsor keeps detailed records of all SAEs reported by the investigators and performs an evaluation with respect to seriousness, causality and expectedness. Adverse events of specific interest and any SAEs as defined above must be reported to the study drug manufacturer (Pharmacosmos®) within 24 hours after the site has gained knowledge of the event in question.

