### 8.4.2 Suspected unexpected serious adverse reactions

---

SUSARs will be reported to the Norwegian Medicines Agency and the Ethics Committee according to national regulation. The following timelines should be followed:

The sponsor will ensure that all relevant information about suspected serious unexpected adverse reactions that are fatal or life-threatening is recorded and reported as soon as possible to the Norwegian Medicines Agency and the Regional Committee for Medical and Health Research Ethics in any case no later than seven (7) days after knowledge by the sponsor of such a case, and that relevant follow-up information is subsequently communicated within an additional eight (8) days. The sponsor shall ensure that suspected adverse reactions that are serious and unexpected are reported to the Norwegian Medicines Agency and to the Regional Committee for Medical and Health Research Ethics within 15 days of the sponsor after knowledge of the event. The sponsor shall inform all investigators of the trial substance in question of suspected adverse reactions that are serious and unexpected. An account of any interruption in treatment or any breaking of the treatment code, the investigator's assessment of the causal relationship, and consequences for further testing shall accompany the notification of suspected adverse reactions pursuant to the first and second paragraphs.

The Norwegian Medicines Agency may require that individual reports of adverse events described in collective reports should also be submitted. The sponsor shall keep detailed records of all adverse events that are reported to him by the investigator. The records shall be submitted to the Norwegian Medicines Agency on request.

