#### **10.2.3 Blinding and emergency un-blinding**

---

The study participants (patients) and all study personnel, including investigators, personnel assessing outcomes, study nurses, data analysts and treating physicians and nurses, will be blinded to allocation to study drug. Only the non-investigating nurse(s) preparing and administering the study drug at randomisation will be aware of treatment allocation.

Un-blinding will be performed in the event of AEs where knowledge of the type of drug might be of importance to the personnel treating the patients, and in the event of SUSARS. Un-blinding will be performed by non-investigating personnel without competing interest, and the result will immediately be reported to the primary investigator, who will then take the required action(s). Unless unavoidable, other investigators and personnel assessing outcomes should not be made aware of treatment allocation.

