7.1 Timing of Analyses

The final analysis will be performed after the last patient has completed the last (6-month) follow-up visit, and all data have been transferred to a separate file on having been documented as meeting the cleaning and approval requirements of the primary investigator and after the finalisation and approval of this Statistical Analysis Plan. Only when these requirements have been met, will database lock occur, and the randomisation code be opened.

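### Protocol 8.1.4 contradicts itself on whether a SUSAR needs a possible causal link, and the literal reading un-blinds unrelated SAEs to the primary investigator

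*Protocol*

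**What the plan says.** Protocol 8.1.4 builds its definitions in steps. An adverse reaction covers "all untoward and unintended responses to an investigational medicinal product related to any dose administered". It is unexpected when its nature or severity does not fit the product information. A SUSAR is then an "SAE (see section 8.1.3) that is unexpected and possibly related to the investigational medicinal products". The next sentence reads: "Any SAE not mentioned in the investigational medicinal product SPC, paragraph 4.8, is to be considered a suspected unexpected serious adverse reaction (SUSAR".

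An SAE itself carries no causality condition (Protocol 8.1.3). One qualifying criterion is that the event "Requires in-patient hospitalisation or prolongation of existing hospitalisation".

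Protocol 8.3 has the investigator grade causality on a scale that includes unrelated and unlikely. Under 8.4.1 the sponsor "performs an evaluation with respect to seriousness, causality and expectedness" for the SAEs reported to it. Under 8.4.2 the sponsor ensures that "suspected adverse reactions that are serious and unexpected are reported to the Norwegian Medicines Agency" and to the ethics committee.

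Protocol 10.2.3 orders un-blinding when a SUSAR occurs, and also when treating staff may need to know the drug. People outside the investigating team break the code, "and the result will immediately be reported to the primary investigator, who will then take the required action(s"). Other investigators and outcome assessors are to remain unaware where possible. SAP 7.1 makes lock and opening of the code wait until the data are documented as "meeting the cleaning and approval requirements of the primary investigator".

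**The concern.** Site staff sorting a serious event need one rule. Here they have two, and the second is the more concrete: look the event up in the SPC list and, if it is absent, call it a SUSAR. Staff who apply it never ask about causality.

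Two things are at stake. The first is the blind. Un-blinding in 10.2.3 hangs on the SUSAR label, so a wider label means more allocations disclosed, during the trial, to the person whose requirements the data must meet before lock. SAP 7.2 also wants exercise-test adequacy and membership of each analysis population settled before the code is opened. That safeguard is weaker if one senior person already knows some allocations.

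The second is reporting. If unrelated events go to the authorities as SUSARs, the expedited reports that matter are mixed with ones that do not.

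The population makes the question a practical one. The protocol's introduction names infections, cancers and rejection as important complications after heart transplantation, and events are collected for six months after the infusion (Protocol 8.2).

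**Working it through.** The plan states no figure on this point, so there is nothing to reproduce. The check is a comparison of texts, followed by an illustration of scale.

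**Step 1: apply both sentences of 8.1.4 to the same events.** Sentence A is the definition with the causality condition. Sentence B is the one that follows it.

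| SAE | Sentence A | Sentence B |
|---|---|---|
| Not in SPC 4.8; graded possible, probable or definite | SUSAR | SUSAR |
| Not in SPC 4.8; graded unrelated or unlikely | Not a SUSAR | SUSAR |
| In SPC 4.8, but of inconsistent severity; possibly related | SUSAR, through the nature-or-severity test | Silent |
| In SPC 4.8 and consistent with it | Not a SUSAR | Silent |

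The second row is the contradiction. The third row shows that a repair based only on whether an event is listed would lose a criterion that 8.1.4 already has.

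**Step 2: does another section settle the second row?**

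- 8.3 records the causality grade but attaches no SUSAR consequence to it.
- 8.4.1 has the sponsor evaluate causality but does not say that this evaluation overrides 8.1.4.
- 8.4.2 sets its timelines for suspected adverse reactions, which points to sentence A. It also opens by using the term SUSAR, and so takes over the ambiguity.
- 8.5 contains only an instruction to supply code-break information and a pointer to 10.2.3.

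The surrounding text leans towards sentence A, but no section says which sentence prevails.

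**Step 3: follow the literal reading.** Unlisted and unrelated SAE → SUSAR (8.1.4, sentence B) → code broken (10.2.3) → result to the primary investigator (10.2.3) → data must meet the same person's requirements before lock (SAP 7.1).

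**Step 4: illustrate the scale.** The planned number of patients is 100 (Protocol 4.2). Two inputs are assumptions, because the documents do not give them: the share of patients with at least one unlisted SAE in six months, *r* = 5-30%, and the share of those judged possibly related or more, *c* = 0-25%.

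- Literal rule: 100 × *r*, from 100 × 0.05 = 5 to 100 × 0.30 = 30 patients un-blinded.
- Causality required: 100 × *r* × *c*, from 100 × 0.05 × 0 = 0 to 100 × 0.30 × 0.25 = 7.5, about 8 patients.
- Difference: 100 × *r* × (1 − *c*), from 100 × 0.05 × 0.75 = 3.75 to 100 × 0.30 × 1 = 30, so about 4 to 30 patients un-blinded only because causality was not asked.

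**The case against.** The strongest reply is that sentence B was meant only to name the reference list for expectedness and presupposes an event already thought possibly related. The sequence of definitions supports this, since adverse reaction, unexpected reaction and SUSAR each narrow the one before. So does 8.4.1: a sponsor causality review would decide nothing for unlisted events if all of them were SUSARs automatically. This is a fair account of the likely intent. It does not remove the conflict, because unexpectedness has already been defined one paragraph earlier, and sentence B says that the event is to be classed as a SUSAR, not merely as unexpected.

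Four stronger conclusions are tempting, and the documents do not support them.

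- *The protocol drops causality from its SUSAR rule.* It does not. Sentence A and sections 8.3, 8.4.1 and 8.4.2 all keep it. The fault is a contradiction.
- *Blinding fails generally.* Section 10.2.3 uses non-investigating staff to break the code and shields other investigators and outcome assessors as far as possible. The exposure is knowledge of individual allocations by one person. The documents do not say that this person judges exercise-test adequacy, and Protocol 7.1.1 gives numerical criteria for it (Borg score above 18 and/or respiratory exchange ratio above 1.05).
- *A true safety signal would be hidden.* Causality is recorded for each event (8.3), and an independent clinician with access to the code receives scheduled safety reports and more on request (8.6). Dilution of expedited reports is possible; concealment is not shown.
- *Most serious events in these patients would be unlisted.* That depends on SPC paragraph 4.8, which is not in the documents. Nor is every admission an SAE: 8.1.3 excludes administrative stays unless an adverse event warrants them.

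**Conclusion.** The point holds as an internal contradiction in Protocol 8.1.4. For an unlisted SAE judged unrelated or unlikely to be related, consecutive sentences give opposite answers, and nothing elsewhere decides between them. Taken literally with 10.2.3, the second sentence discloses allocations for unrelated events to the primary investigator before lock.

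The contradiction is certain on the text. Its practical size is not. It depends on which sentence staff follow, on how many patients have an unlisted SAE, and on how many of those events are judged related. The ranges of 5-30 and about 0-8 patients out of 100 rest wholly on the assumed rates and count each affected patient once. They are not forecasts. No particular data decision can be shown to be biased, so this is a weakness in the protection of the blind rather than a demonstrated bias in the primary result. It should be corrected because the ambiguity is avoidable and the repair is small.

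**What to change.** Replace the second sentence, so that the SPC serves only to judge expectedness and the causality condition stays. For example: *An SAE assessed as possibly, probably or definitely related (sections 8.3 and 8.4.1), whose nature or severity is not consistent with SPC paragraph 4.8, is a SUSAR.* Because 8.3 is the investigator's assessment and 8.4.1 the sponsor's, the text should also say which counts when they differ.

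Add a statement that this single definition governs both expedited reporting (8.4.2) and SUSAR un-blinding (10.2.3). The separate un-blinding route in 10.2.3, for events where treating staff may need to know the drug, is not affected.

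The cost is one replaced sentence, a short clarification and a cross-reference, handled as a protocol amendment under section 11.3. There is no effect on sample size, visits or analysis. Compared with the literal reading, it means fewer code breaks and fewer expedited reports. The change does not alter who receives the result when a SUSAR meeting the definition is un-blinded; that stays with the primary investigator.
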